14.6 Efficacy Analysis

Secondary endpoints will be used to gain preliminary estimates of efficacy. The analyses of secondary endpoints will be based on patients enrolled in the expansion cohorts and will be summarized within disease type. ORR will be estimated for each disease cohort and will be summarized with 90% confidence intervals estimated using exact binomial methods. For samples of size 12, the confidence intervals will be no wider than 0.5. Time-to-event endpoints (i.e., PFS, OS, TTP) will be summarized using the product-limit method of Kaplan-Meier; confidence intervals will be based on log(-log(survival)) methodology. Six-month PFS, 12-month OS, and median TTP will be presented, by disease, with 90% confidence intervals. With few patients in each disease, statistical testing will be of low power. Therefore, the analyses within disease will be primarily descriptive and will not rely on p-values.

14.7 Safety Analysis

Safety data will be presented for all patients who receive at least one dose of either of the study drugs. All adverse events recorded during the trial will be summarized and presented by disease cohort or dose level. The incidence of events that are new or worsening from the time of first dose of treatment will be summarized by dose level or disease cohort, system organ class and/or preferred term, severity (based on CTCAE V4 grade), type of adverse event, and relation to study treatment. Deaths reportable as SAEs and non-fatal serious adverse events will be listed by patient and tabulated by primary system organ class, and type of adverse event.

Safety data from the expansion cohorts will be used to further characterize the safety profile of the drug combination and evaluate the toxicity of the MTD from the dose escalation. We assume that toxicities will be similar for each of the expansion cohorts; however, we will summarize safety data in both the aggregate and by cohort to allow for different adverse event types. Late toxicities observed and assessed as treatment related in the expansion cohort will be monitored. If two or more are observed, enrollment in the expansion cohort will be halted for further review and changing the RP2D will be considered. Given that trebananib is limited in use during only the first 12 weeks (4 cycles), we anticipate there is less chance that the combination of trebananib plus pembrolizumab will exhibit late toxicity in comparison to pembrolizumab given alone.

The following table summarizes the probability of observing at least one patient with a treatment-related toxicity for varying true, but unknown, incidence rates. Estimates in the table are based on individual expansion cohorts of size 12, and also for all 48 patients treated at the MTD.

Underlying incidence rate of treatment-related toxicity	Probability of 1 or more of 12 with treatment-related toxicity	Probability of 1 or more of 48 with treatment-related toxicity
0.01	0.11	0.38
0.05	0.46	0.91
0.10	0.72	0.99
0.15	0.86	>0.99
0.20	0.93	>0.99
0.25	0.97	>0.99

For each expansion cohort of size 12, the probability of observing at least one patient with a dose-related toxicity is greater than 0.70 if the incidence rate of that toxicity is 0.10 or higher. For the aggregated safety data, there is greater than 0.90 probability of observing a toxicity if the incidence rate is 0.05 or higher.

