1. OBJECTIVES

1.1 Study Design

This is a prospective trial which will accrue participants with solid tumors to evaluate the safety, clinical, and immunological effect of the combination of pembrolizumab (MK-3475) and trebananib (AMG386). The treatment will include an induction phase of pembrolizumab and trebananib for 4 cycles (12 weeks) followed by pembrolizumab alone for 2 years. The study will accrue up to 60 participants. This trial will be conducted in 2 parts. Part I will use a standard 3+3 dose escalation design in all solid tumors. The goal of Part I will be to identify the recommended part 2 (expansion cohort) doses (RP2D) for the combination of pembrolizumab plus trebananib. Dose escalation will begin in dose cohort +1. If two or more patients in dose cohort +1 experience a DLT, the next cohort of patients will be enrolled into dose cohort -1. Should dose cohort -1 prove too toxic, enrollment to the study will stop. If the toxicity profile of dose cohort +1 is acceptable, the next cohort will be enrolled into dose cohort +2. Should dose cohort +2 have acceptable toxicity, that will be the RP2D; otherwise, dose cohort +1 will be the RP2D.

Part II has 4 dose expansion cohorts to be treated at the RP2D, which was determined to be 200 mg pembrolizumab every 3 weeks + 30 mg/kg trebananib every week:

- melanoma
- renal cell carcinoma (RCC)
- ovarian cancer
- colorectal cancer (CRC)

Initially, 12 patients were to be treated in each cohort. However, as of protocol amendment Version 4.0, no patients were enrolled to the melanoma cohort and only 4 patients were enrolled to the RCC cohort. Due to slow accrual in these specific cohorts, the melanoma and RCC cohorts will no longer be open to accrual. Accrual will continue in the ovarian cohort, and the CRC cohort will be expanded to allow enrollment of 37 patients total.

Safety assessments will include all patients receiving one or more doses of the study drug combinations. Secondary and correlative endpoints will be based on the cohorts of patients enrolled in Part II of the trial. We will summarize secondary and correlative endpoints according to disease indication and, in an exploratory fashion, with all patients combined. Pre-and on-treatment biopsies will be obtained for all patients enrolled in the dose expansion cohorts and archival tissue will be collected for selected dose escalation patients when available.

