1.2 Primary Objectives

- Part 1: To determine the safety, tolerability, and RP2D for trebananib when given with pembrolizumab in patients with metastatic solid tumor.
- Part 2 (expansion cohort): To determine the safety and tolerability of the RP2D of trebananib, determined in Part 1, when given with pembrolizumab in patients

with unresectable stage III or stage IV melanoma, metastatic renal cell, ovarian, or colorectal cancer.

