5.2 Trial Treatments

The treatment to be used in this trial is outlined below in Table 4. Each treatment cycle will be 3 weeks (21 days) long.

The treatment will include an induction phase of pembrolizumab and trebananib for 4 cycles (12 wks) followed by pembrolizumab alone for 2 years.

Table 4. Regimen Description for Parts I and II

Regimen Description					
Agent	Pre-medications	Dose	Route	Schedule ***	Cycle Length
Pembrolizumab	Not routinely necessary unless prior infusion reaction	200mg at a final concentration of 1 mg/mL to 10 mg/mL in NS or D5	IV over approximately 30 minutes (range: 25-40 minutes)	Day 1	21 days (3 weeks)
Trebananib	Not routinely necessary unless prior infusion reaction	** mg/kg at a final concentration of 30mg/mL in NS	****IV over approximately 30 minutes	Day 1,8,15	
**Doses as appropriate for assigned dose level.					
*** The treatment will include an induction phase of pembrolizumab and trebananib for 4 cycles (12 wks) followed by pembrolizumab alone for 2 years.					

**** First dose of trebananib should be administered over 60 minutes.

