- Noncompliance with trial treatment or procedure requirements
- The participant is lost to follow up.
- The participant completes 24 months of uninterrupted treatment with pembrolizumab or 35 administrations of study pembrolizumab, whichever is later
- Administrative reasons
- Unacceptable adverse event(s), including:
 - Any Grade 2 drug-related uveitis or eye pain or blurred vision that does not respond to topical therapy and does not improve to Grade 1 severity within the re-treatment period OR requires systemic treatment
 - Grade 3 drug-related autoimmune or inflammatory event including uveitis, pneumonitis, diarrhea, colitis, neurologic adverse events, hypersensitivity reaction, or infusion reaction of any duration requires discontinuation.
 - Any Grade 3 or 4 drug-related laboratory imbalance or electrolyte abnormality, not associated with underlying organ pathology and that do not require treatment except for electrolyte replacements do not require treatment discontinuation, with the following exceptions with approval of the Principal Investigator:
 - Hypophysitis or pan-hypopituitarism any grade should discontinue treatment.
 - Grade 4 amylase or lipase abnormalities that are not associated with DM, associated liver or gall bladder inflammation clinical manifestations of pancreatitis may stay on study.
 - Any drug-related liver function test (LFT) abnormality that meets the following criteria requires discontinuation: Grade 4 AST or ALT.

- Grade 3 drug-related thrombocytopenia >7 days or associated with bleeding requires discontinuation.
- For patients with skin-only toxicity, when symptoms improve to Grade 1 or less, steroid taper should be started and continued over no less than 4 weeks. Discontinue pembrolizumab if unable to reduce corticosteroid dose for irAEs to ≤ 10 mg. Pembrolizumab treatment may be restarted and the dose modified as specified in the protocol.
- Patients with endocrinopathy (e.g. thyroiditis, hypophysitis) and no other autoimmune/inflammatory event may be restarted after a short course of steroids and/or on a stable replacement regimen.
- Any dosing interruption lasting >12 weeks with the following exceptions:
 - Dosing interruptions >12 weeks that occur for non-drug-related reasons may be allowed if approved by the Principal Investigator. Prior to re-initiating treatment in a participant with a dosing interruption lasting >12 weeks, the Principal Investigator must be consulted.

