	† Results in or prolongs an existing inpatient hospitalization (hospitalization is defined as an inpatient admission, regardless of length of stay, even if the hospitalization is a precautionary measure for continued observation. (Note: Hospitalization for an elective procedure to treat a pre-existing condition that has not worsened is not a serious adverse event. A pre-existing condition is a clinical condition that is diagnosed prior to the use of a Merck product and is documented in the patient's medical history.); or	
	† Is a congenital anomaly/birth defect (in offspring of participant taking the product regardless of time to diagnosis); or	
	Is a new cancer (that is not a condition of the study) (although not serious per ICH definition, is reportable to the IND holder within 24 hours and to Merck within 2 working days to meet certain local requirements); or	
	Is an overdose (whether accidental or intentional). Any adverse event associated with an overdose is considered a serious adverse event for collection purposes. An overdose that is not associated with an adverse event is considered a non-serious event of clinical interest and must be reported within 24 hours to the Sponsor and to Merck within 2 working days.	
	Other important medical events that may not result in death, not be life threatening, or not require hospitalization may be considered a serious adverse event when, based upon appropriate medical judgment, the event may jeopardize the participant and may require medical or surgical intervention to prevent one of the outcomes listed previously (designated above by a †).	
Duration	Record the start and stop dates of the adverse event. If less than 1 day, indicate the appropriate length of time and units	
Action taken	Did the adverse event cause Merck product to be discontinued?	

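### Section 14.7 tabulates adverse events over the whole regimen with no split at the end of trebananib, so the tables do not show the safety of the trebananib-containing period

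*Combined protocol and SAP*

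**What the plan says.** The Part 2 primary objective in Section 1.2 reads: "To determine the safety and tolerability of the RP2D of trebananib, determined in Part 1, when given with pembrolizumab in patients", followed by the tumor types. Section 14.7 gives the expansion data the same purpose: "Safety data from the expansion cohorts will be used to further characterize the safety profile of the drug combination".

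The two drugs run for very different times. Section 5.2: "The treatment will include an induction phase of pembrolizumab and trebananib for 4 cycles (12 wks) followed by pembrolizumab alone for 2 years". Section 5.12 ends pembrolizumab when: "The participant completes 24 months of uninterrupted treatment with pembrolizumab or 35 administrations of study pembrolizumab, whichever is later". Under Section 5.3.3.2 a patient who permanently stops trebananib may go on with pembrolizumab alone, so the trebananib period can be shorter than 12 weeks. Under Section 5.3.3.1 the reverse is also possible: trebananib may continue alone after pembrolizumab is permanently stopped.

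The analysis in Section 14.7 is: "All adverse events recorded during the trial will be summarized and presented by disease cohort or dose level". New or worsening events are broken down by dose level or cohort, organ class or preferred term, and then "severity (based on CTCAE V4 grade), type of adverse event, and relation to study treatment". Treatment period is not among the dimensions, and no exposure-adjusted rate is planned. The data needed for a split are collected. Table 15 in Section 6.4 instructs: "Record the start and stop dates of the adverse event".

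**The concern.** An event that starts in month 15, long after trebananib has ended, enters the same incidence figure under the same trebananib dose level as one that starts in week 5. The figure then depends partly on how long patients stay on pembrolizumab alone. A reader who wants to know what happened while patients were receiving trebananib with pembrolizumab cannot find it in the planned tables.

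The coding of relation to treatment does not clearly fill the gap. Section 6.4 grades relation to the study treatment as a whole, and Table 15 then asks about the Merck product only. Section 5.3.3.1 lets the investigator attribute an event to one drug or to the combination, but Section 14.7 does not commit to tabulating by drug.

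**Working it through.** **The plan's own figures.** Section 14.7 gives no figure for the split. Its one table, the probability of seeing at least one patient with a toxicity, is 1 − (1 − p)^n and reproduces in every cell. For p = 0.01, 0.05, 0.10, 0.15, 0.20 and 0.25, n = 12 gives 0.114, 0.460, 0.718, 0.858, 0.931 and 0.968; n = 48 gives 0.383, 0.915, 0.994 and then above 0.999. The arithmetic is right. The table states no time window for the toxicity rate.

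**Inputs for the share of time without trebananib.**
- Induction: 12 weeks (Sections 1.1 and 5.2).
- Pembrolizumab: 24 months or 35 administrations (Section 5.12), taken as 104 weeks.
- Retention: about 40% complete 24 weeks (Section 14.8).
- Allowance: 30 days, as in the adverse event collection window of Section 6. Counted from week 12, it ends at 12 + 30/7 = 16.3 weeks.
- Assumption: the shape of the dropout curve, which the documents do not give.

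**A patient who completes treatment.** Trebananib is given in 4 of 35 cycles, or 11.4%.

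**Constant dropout (assumed).** Hazard h = −ln(0.4)/24 = 0.0382 per week. Mean treatment time to week t is (1 − exp(−ht))/h:
- to week 12: 9.63 weeks
- to week 16.3: 12.13 weeks
- to week 104: 25.70 weeks

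Share without trebananib: 1 − 9.63/25.70 = 63%. With the allowance: 1 − 12.13/25.70 = 53%.

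**Other dropout shapes.** Take Weibull survival S(t) = exp(−(t/b)^k) with b = 24/(−ln 0.4)^(1/k), so that 40% remain at week 24. Mean time is the integral of S(t):

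| Shape k | Mean to wk 12 | to wk 16.3 | to wk 104 | Share without trebananib | With 30-day allowance |
|---|---|---|---|---|---|
| 2 | 11.14 | 14.26 | 22.22 | 50% | 36% |
| 1 (constant) | 9.63 | 12.13 | 25.70 | 63% | 53% |
| 0.6 | 8.32 | 10.52 | 30.82 | 73% | 66% |

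The last scheduled trebananib dose is Cycle 4 Day 15, which is day 63 + 15 = 78. Counting the 30 days from that dose ends the window at 108/7 = 15.4 weeks and raises the last column by about 1 to 3 percentage points.

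**Illustration from the interim colorectal data (Section 14.2).** Of 15 patients, 1 had a partial response and 4 had stable disease for a median of 10 months. Assume these 5 stay on treatment for 10 months (43.3 weeks) and the other 10 stop at week 12. Total time is 10 × 12 + 5 × 43.3 = 336.7 patient-weeks, of which 15 × 12 = 180 is induction. The share without trebananib is 1 − 180/336.7 = 47%. With the allowance it is 1 − (120 + 5 × 16.3)/336.7 = 40%.

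**Why this is not a share of events.** Moving from exposure to events needs a second assumption. Suppose an event has a constant hazard and a 5% risk over 12 weeks, so g = −ln(0.95)/12 = 0.00427 per week. With the constant dropout above, observed incidence by week t is g/(g + h) × (1 − exp(−(g + h)t)): 4.0% by week 12 and 9.9% by week 104. About 60% of first events would then start after week 12. Events concentrated early would give a smaller share.

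**The case against.** The treatment under test is a sequence, induction followed by pembrolizumab, so incidence over the whole sequence is a legitimate summary. The DLT rate lies wholly inside combination dosing (Section 5.5), and the RP2D is already set. Section 14.4 summarizes cycles and dose intensity for both drugs. Section 14.7 itself notes the 12-week limit and monitors late treatment-related toxicity. The split can also be produced at reporting from dates already held. All of this stands and limits the consequence. It does not supply the missing table: Section 14.4 does not link events to period, and Section 14.7 does not define what counts as late.

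Several stronger readings are tempting, and the documents do not support them:
- *Attribution by drug is useless throughout.* The sentence in Section 5.3.3.1 about difficulty applies when the drugs are given together. It does not describe an event in month 15 of pembrolizumab alone.
- *The trebananib period should be the sole basis for the RP2D safety statement.* Section 5.3.3.1 says immune-related events may appear several months after the last dose, and Section 14.7 uses late toxicity to reconsider the RP2D. That basis would drop events the plan wants to count.
- *The first period is pure combination.* Trebananib may continue alone, so trebananib-containing is the correct label.
- *A split would reveal what trebananib adds.* The trial has no control group, and both drugs are normally present in the first period.
- *Cohorts with longer disease control will be judged more toxic.* No formal safety comparison between cohorts is planned; melanoma is closed without patients and RCC has four.

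**Conclusion.** The gap is real and worth closing, as an inexpensive improvement rather than the correction of an error. The planned tables describe the whole regimen and leave the trebananib-containing period, the subject of the Part 2 primary objective, unreported on its own. The pooled tables remain valid.

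Under 40% retention at 24 weeks, between 50% and 73% of treatment time is without trebananib (36% to 66% with the 30-day allowance). The interim colorectal illustration gives 47% (40%). The single value of 63% should not be quoted alone. It rests on constant dropout, while scans every 12 weeks would tend to bunch progression stops near week 12. The 40% figure was also set for 48 patients in four disease groups, whereas Section 14.2 now plans 53 patients, most of them colorectal. A reader might take 63% to mean that most reported events belong to pembrolizumab alone. The figure measures exposure and does not show that. The absence of a split does not depend on any of these assumptions.

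**What to change.** Keep the pooled tables in Section 14.7 and add adverse event tables by period of onset:

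1. Trebananib-containing period: from first dose to 30 days after that patient's last trebananib dose.
2. Thereafter.

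Give the number at risk and the person-time in each period. State that the RP2D safety and tolerability conclusion reports both periods together and does not rest on the first alone, because delayed immune events from the combination may begin in the second.

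The cost is a few lines of text and one extra set of tables. No new data, patients or visits are needed, since event start dates and trebananib dosing dates are recorded. The split must be labelled descriptive because the two periods are not comparable populations. The first can end because of trebananib toxicity, and the second contains only patients who remain under observation. Adverse event review also falls from Days 1, 8 and 15 of each cycle to Day 1 only (Section 9). The added tables show when events began; they do not isolate trebananib's own contribution.

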14.8 Proposed analyses of correlative endpoints

For the analysis of cytokines, chemokines, and immune cell populations from serum or blood, data will be combined from all four disease groups according to treatment, resulting in longitudinal measurements for approximately 48 patients. Serum marker levels will be summarized descriptively and graphically. The time course of expression levels will also be summarized graphically by patient, noting disease group and times of disease progression. Since patients may have rapid disease progression and terminate treatment early, the use of linear mixed models includes partial data in the analysis allowing characterization of outcome. Transformations will be applied to the outcome measures to stabilize variability and normalize the distributions, when appropriate.

In an exploratory analysis, we will summarize changes in biomarker levels in the subsets of patients who complete 6 months of treatment, recognizing that this may be a select group of participants with less severe disease. Fold-changes will be calculated comparing 6-month and pre-treatment levels (6-month/pre) and summarized descriptively. We estimate that approximately 40% of patients will complete 24 weeks of treatment, resulting in 19-20 patients.

Biomarkers from tissue will be assessed using IHC. Analyses relating baseline expression levels with response will be based on approximately 48 patient samples from newly obtained excisional biopsies or archival tissue. Paired biopsies will be needed from 20 patients in the dose expansion cohort, ideally 5 per disease indication. An endpoint of interest in the tissue analysis would be the proportion of patients with at least a 50% decrease in CD137 M2 macrophages. We anticipate a null proportion of 0.20 with at least a 50% decrease. The combination of trebananib with pembrolizumab would show important biomarker response if the proportion with 50% decrease in CD137 M2 macrophages is at least 0.45. With 20 paired biopsies, an exact binomial test with nominal, two-sided, 0.1-significance level will have at least 80% power to detect the difference between proportions of 0.20 and 0.47.

15. PUBLICATION PLAN

The results should be made public within 24 months of reaching the end of the study. The end of the study is the time point at which the last data items are to be reported, or after the outcome data

are sufficiently mature for analysis, as defined in the section on Sample Size, Accrual Rate and Study Duration. If a report is planned to be published in a peer-reviewed journal, then that initial release may be an abstract that meets the requirements of the International Committee of Medical Journal Editors. A full report of the outcomes should be made public no later than three (3) years after the end of the study.

APPENDIX A PERFORMANCE STATUS CRITERIA

ECOG Performance Status

Grade	Description
0	Normal activity. Fully active, able to carry on all pre-disease performance without restriction.
1	Symptoms, but ambulatory. Restricted in physically strenuous activity, but ambulatory and able to carry out work of a light or sedentary nature (e.g., light housework, office work).
2	In bed <50% of the time. Ambulatory and capable of all self-care, but unable to carry out any work activities. Up and about more than 50% of waking hours.
3	In bed >50% of the time. Capable of only limited self-care, confined to bed or chair more than 50% of waking hours.
4	100% bedridden. Completely disabled. Cannot carry on any self-care. Totally confined to bed or chair.
5	Dead.
* As published in Am. J. Clin. Oncol.: Oken, M.M., Creech, R.H., Tormey, D.C., Horton, J., Davis, T.E., McFadden, E.T., Carbone, P.P.: Toxicity And Response Criteria Of The Eastern Cooperative Oncology Group. Am J Clin Oncol 5:649-655, 1982. The Eastern Cooperative Oncology Group, Robert Comis M.D., Group Chair.
